### **7.11.3 Additional Effectiveness Endpoints**

The additional effectiveness endpoints will be summarized descriptively in the PP and mITT analysis sets after all study subjects completed their 12-month follow up.

- **Single Procedural Success:** The number and percentage of subjects with single procedural success will be summarized. Kaplan-Meier estimates and plots will be used to characterize the time to first documented symptomatic atrial arrhythmia (AF, AT or AFL) recurrence following a single index ablation procedure.
- **Freedom from documented symptomatic atrial arrhythmia (AF, AT or AFL of unknown origin\*):** Kaplan-Meier estimates and plots will be used to characterize the time to first documented symptomatic atrial arrhythmia (AF, AT or AFL of unknown origin\*) recurrence based on electrocardiographic data ( $\geq 30$  seconds on arrhythmia monitoring device) during the effectiveness evaluation period (Day 91-Day 365).
- **Freedom from documented (symptomatic and asymptomatic) atrial arrhythmia (AF, AT or AFL of unknown origin\*) with additional failure modes:** Kaplan-Meier estimates and plots will be used to characterize the time to first documented (symptomatic and asymptomatic) atrial arrhythmia (AF, AT or AFL of unknown origin\*) based on electrocardiographic data ( $\geq 30$  seconds on arrhythmia monitoring device) during the effectiveness evaluation period (Day 91-Day 365).

The event-free rate will also be summarized descriptively as the number and percent of subjects free from documented (symptomatic and asymptomatic) atrial arrhythmia (AF, AT or AFL of unknown origin\*) during the evaluation period.

- **Use of a non-study device:**

- The number and percentage of subjects and number and percent of PVs ablated by a non-study catheter (NSC) for PVI will be summarized.

- Rate of ablation by NSC for PVI among all targeted pulmonary veins during index procedure:

$$= \frac{\text{Number of PVs ablated by NSC}}{\text{Number of ablated PVs}}$$

- Rate of ablation by NSC for PVI among subjects during index procedure:

$$= \frac{\text{Number of subjects with at least one PV ablated by NSC}}{\text{Total number of subjects ablated for PVI}}$$

- Ablation of left atrial non-PV AF targets (i.e., posterior wall) during index ablation procedure or for repeat procedures during the blanking period.

$$= \frac{\text{Number of subjects with left atrial non - PV AF targets ablated by NSC}}{\text{Total number of subjects ablated for left atrial non - PV AF targets}}$$

- **Acute reconnection:**

- Rate of acute PV reconnection among targeted veins:

$$= \frac{\text{Number of targeted veins with PV reconnection after adenosine/isoproterenol challenge}}{\text{Total number of targeted veins with adenosine/isoproterenol challenge}}$$

- Rate of acute PV reconnection among subjects:

$$= \frac{\text{Number of subjects with PV reconnection in at least one PV after adenosine/isoproterenol challenge}}{\text{Total number of subjects undergone PV ablation procedure and adenosine/isoproterenol challenge}}$$

- **Repeat ablation procedures-related endpoints:**

- Kaplan-Meir estimates and plot will be used characterize the time to the first repeat ablation within the 12-month FU period.
  - Additionally, percentages of subjects with repeat ablation will be summarized by timing of occurrence, including:

1. Percentage of subjects with repeat ablation during blanking period ( $\leq 90$  days post index ablation procedure)

$$= \frac{\text{Number of subjects undergoing repeat ablation for left atrial arrhythmia during blanking}}{\text{Total number of subjects undergone index ablation procedure}}$$

2. Percentage of subjects with repeat ablation after blanking period (Day 91 – follow-up 365 post index ablation procedure)

$$= \frac{\text{Number of subjects undergoing repeat ablation for left atrial arrhythmia after blanking}}{\text{Total number of subjects undergone index ablation procedure}}$$

- PV reconnection identified during the repeat procedure will be summarized:

1. Rate of PV reconnection among previously isolated veins (index):

$$= \frac{\text{Number of previously isolated veins (index) with PV reconnection at repeat procedure}}{\text{Total number of previously isolated veins (index) in subjects who undergo repeat ablation procedure}}$$

2. Rate of PV reconnection among subjects:

$$= \frac{\text{Number of subjects with PV reconnection at repeat procedure}}{\text{Total number of subjects undergone repeat ablation procedure with PVI at index}}$$

- Repeat ablation due to non-PV targets: percentage of subjects with repeat ablations due to non- PV targets

$$= \frac{\text{Number of subjects with non - PV reconnection at repeat procedure}}{\text{Total number of subjects undergone repeat ablation procedure}}$$

- **Quality of Life (QoL) :**

Baseline AFEQT scores and changes from baseline at each timepoint the questionnaire is administered will be summarized descriptively for the following five scores. The overall AFEQT score and subscale scores across study visits will also be plotted.

- Overall AFEQT Score (18 questions)
  - Symptom Subscale Score (4 questions)
  - Daily Activities Subscale Score (8 questions)
  - Treatment Concern Subscale Score (6 questions)

- Treatment Satisfaction Score (2 questions)
- **Hospitalization for cardiovascular events:** The number and percentage of subjects and number and percent of hospitalization for cardiovascular event will be summarized.

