7.3.3 Additional Effectiveness Endpoints

PVI Durability Rate

- Percentage of targeted PVs in the index ablation procedure being durably isolated as confirmed by the electroanatomical mapping 75 days (+/- 15days) post index ablation procedure.
- Percentage of subjects with durably isolated targeted PVs as confirmed by the electroanatomical mapping at 75 days (+/- 15days) post index ablation procedure.

Single Procedural Success: defined as freedom from documented symptomatic atrial arrhythmia (AF, AT or AFL of unknown origin*) episodes based on electrocardiographic data (≥ 30 seconds on arrhythmia monitoring device) during the effectiveness evaluation period (Day 91-Day 365) following a single index ablation procedure.

Freedom from documented symptomatic atrial arrhythmia (AF, AT or AFL of unknown origin *) episodes based on electrocardiographic data (≥ 30 seconds on arrhythmia monitoring device) during the effectiveness evaluation period (Day 91-Day 365). Acute procedural failure will also be considered failure of 12-month symptomatic recurrence free endpoint.

Freedom from documented (symptomatic and asymptomatic) atrial arrhythmia (AF, AT or AFL of unknown origin*) episodes based on electrocardiographic data (≥ 30 seconds on arrhythmia monitoring device) during the effectiveness evaluation period (Day 91-Day 365) with extra failure modes. A subject who meets any of the following criteria will also be deemed an effectiveness failure:

- Failure to achieve acute procedural success.
- Taking a new Antiarrhythmic Drug (AAD) (Class I / Class III) for atrial tachyarrhythmia (AF, AT or AFL of unknown origin*) or taking a previously failed Class I/III AAD at a greater than the highest ineffective historical dose for AF/AFL/AT during the effectiveness evaluation period (Day of 3-month visit – Day 365).
- Greater than 1 repeat ablation for AF/AT or AFL of unknown origin* in the blanking period or any repeat ablation for AF/AT or AFL of unknown origin* during the effectiveness evaluation period.

Use of a non-study device for the purpose of:

- PVI (i.e., touch-up) among all clinically relevant targeted PVs and by subject
- Ablation of left atrial non-PV AF targets (i.e., posterior wall) during index ablation procedure or for repeat procedures during blanking period.

Acute reconnection identified by adenosine/isoproterenol challenge among all clinically relevant targeted PVs

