Recurrence of AF/AT/AFL	Recurrence of AF/AFL/AT post-ablation is defined as a recurrence of atrial fibrillation more than 3 months following AF ablation. Episodes of atrial tachycardia or atrial flutter should also be classified as a "recurrence." Electrocardiographical occurrences of new onset non left atrial arrhythmia's, if confirmed by entrainment maneuvers during electrophysiology testing, should not be considered an ablation failure or primary effectiveness endpoint. Examples are: 
• CTI dependant AFL. Cavotricuspid isthmus-dependent atrial flutter is easily treated with cavotricuspid isthmus ablation and is not an iatrogenic arrhythmia following a left atrial ablation procedure for AF.• Atrioventricular nodal reentry tachycardia (AVNRT)
Off AAD	As assessed from the end of the 3-month blanking period (Day 91 or Day of the visit whatever comes last) to 12 months following the ablation procedure. Class I and III antiarrhythmic drug therapy, same dose as before procedure is not considered as failure Class I and III antiarrhythmic drug therapy, higher dose or newly prescribed after procedure is considered as failure Class I and III antiarrhythmic drug therapy prescribed for other arrhythmia's than AF/AT/AFL is not considered as failure

31 Appendix 3

Table 11: Comprehensive List of Anticipated Adverse Events

Anticipated Adverse Events	
(Acute) renal failure	Infection, systemic
(Aspiration) pneumonia	Inflammation
(Skin) laceration	Isolated ST segment elevation
(Vascular) bleeding	Liver toxicity
Acute Respiratory Distress Syndrome (ARDS)	Local Hematoma/ecchymosis
Air embolism	Localized skin reaction
Allergic reaction to contrast media	Mitral Insufficiency
Allergic skin reaction	Myocardial infarction with or without ST elevation
Altered Mental Status Confusion; Altered Level of Consciousness;	Nausea
Anaphylactic shock	Neurological disorders (poor coordination)
Anemia	Neurological disorders (tremor)
Anesthesia complications/reactions	Neuropapraxia/Muscle contraction
Anoxic or hypoxic encephalopathy	Palpitations
Aortic Puncture	Papillary Muscle tear/injury
Apnea - sedation induced	Pericardial effusion resulting in tamponade
Arrhythmia (new or worsening of pre-existing arrhythmia)	Pericardial effusion without tamponade
Asthmatic attack	Pericarditis
Asymptomatic Cerebral Emboli	Periesophageal vagal nerve injury
Atelectasis	Peripheral nerve injury
Atrial fibrillation	Phlebitis

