**Signature Page**

## Revision History

Revision Number	Revision Date (DD/MMM/YYYY)	Reasons for Revision
V 1.0	13/JUN/2023	Original document: SAP template version 5.0 implemented.
V 2.0	07/NOV/2023	
1. Clarification was added on the definition of Esophageal Endoscopy (EE) analysis set in Section 5.0
 
2. Clarification was provided for different PVI Durability assessment scenarios in Section 7.1.4.
 
3. The analysis sets were modified to match what is specified in the CIP in Section 7.7.1
 
4. The site homogeneity analysis was removed due to not being proposed in CIP.
 
5. The details of operation definition of AAD failure (Day 105-Day 365) was provided. So AAD failure could be systematically evaluated in Section 7.3.4.3.
 
6. Acute procedural success was determined based on the targeted veins in which the entrance block could be determined, not on the clinical relevant PV anatomy in Section 7.3.2.

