### 7.1.3 Handelling Subjects with Specific Ablation Scenarios in Effectiveness Endpoint Analysis

Subjects who undergo ablation using the investigational ablation system or commercial ablation devices at the **PV/CTI regions or outside the PV/CTI regions** will be included in the analysis of acute and long-term effectiveness endpoints according to the following guidelines:

- Condition 1: Subjects who undergo ablation **using the investigational ablation system for PV isolation** will be included in the analysis of acute effectiveness endpoints.
  - If the PV isolation is completed using commercial RF (radiofrequency) devices due to reasons related to the study system (SMARTTOUCH™ SF (STSF) and TRUPULSE™ Generator), the subject will be considered a failure for the acute effectiveness endpoint and be included in acute and long-term effectiveness endpoint analyses..
  - If the PV isolation is completed using commercial RF devices due to reasons unrelated to the study system (SMARTTOUCH™ SF (STSF) and TRUPULSE™ Generator), the subject will be considered not evaluable for the effectiveness of the investigational system and will be excluded from the analyses of acute and long-term effectiveness endpoints.
- Condition 2: The use of the **investigational ablation system outside the PV/CTI region is not permitted** according to the protocol. Subjects who undergo ablation outside the intended regions using investigational ablation system will be excluded from the long-term effectiveness endpoint analysis, unless they have already failed the acute effectiveness endpoint. Subjects who failed the acute effectiveness endpoint will also be considered failures for the long-term effectiveness endpoint.

- Condition 3: In cases where **commercial RF devices are used for ablation outside the PV region and/or CTI line** to treat arrhythmia identified during the procedure, it is allowed for the well-being of the patient. However, these subjects will be excluded from the long-term effectiveness analysis, as they received additional ablations beyond the intended treatment using non-investigational devices. This exclusion is necessary to avoid mixed effects from non-study devices that could confound the interpretation of the long-term effectiveness results for the investigational devices.

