##### 7.4.4.3 Additional Effectiveness Endpoints

- **Single Procedural Success:** defined as freedom from documented symptomatic atrial arrhythmia (AF, AT or AFL of unknown origin\*) episodes based on electrocardiographic data ( $\geq 30$  seconds on arrhythmia monitoring device) during the effectiveness evaluation period (Day 91-Day 365) following a single index ablation procedure. Subjects who had repeat procedure(s) for the study arrhythmia post the index procedure will be deemed failures of this endpoint.
- **Freedom from documented symptomatic atrial arrhythmia (AF, AT or AFL of unknown origin\*):** defined as freedom from the documented symptomatic atrial arrhythmia (AF, AT or AFL of unknown origin\*) recurrence

based on electrocardiographic data ( $\geq 30$  seconds on arrhythmia monitoring device) during the effectiveness evaluation period (Day 91-Day 365).

Acute procedural failure (i.e., failure to confirm entrance block in all PVs except those that are silent and/or cannot be cannulated post-procedure, use of non-study catheter for PV isolation, and failure to have energy delivery with the study device due to ablation system malfunctions) will also be considered a failure.

- **Freedom from documented (symptomatic and asymptomatic) atrial arrhythmia (AF, AT or AFL of unknown origin\*) with additional failure modes:** defined as freedom from documented (symptomatic and asymptomatic) atrial arrhythmia (AF, AT or AFL of unknown origin\*) based on electrocardiographic data ( $\geq 30$  seconds on arrhythmia monitoring device) during the effectiveness evaluation period (Day 91-Day 365). The following criteria will also be deemed failures:
  - Failure to achieve acute procedural success.
  - Taking a new Antiarrhythmic Drug (AAD) (Class I / Class III) for atrial tachyarrhythmia (AF, AT or AFL of unknown origin\*) or taking a previously failed Class I/III AAD at a greater than the highest ineffective historical dose for AF/AFL/AT during the effectiveness evaluation period (Day of 3-month visit\* – Day 365).
  - Greater than 1 repeat ablation for AF/AT or AFL of unknown origin\* in the blanking period or any repeat ablation for AF/AT or AFL of unknown origin\* during the effectiveness evaluation period.

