*\*Note: The upper bound of the 3-month visit will be considered as the start point of the evaluation period of AAD failure, which is Day 105. As it is a common practice for medications to be adjusted and/or stopped during an in-clinic visit (i.e., 3-month follow-up visit), subject may have his/her medication adjusted or stopped during the CIP-defined follow-up window, including the Class I/III AADs.*

- **Use of a non-study device** for the purpose of PVI (i.e., touch-up) and/or for the ablation of left atrial non-PV AF targets (i.e., posterior wall) during index ablation procedure or within-lanking repeat procedures.
- **Acute reconnection:** any reconnection in the PVs that are identified after adenosine/isoproterenol challenge among all targeted PVs.

- **Repeat ablation procedures** for left atrial arrhythmia (AF, AT or AFL of unknown origin\*) within the 12-month FU period. Procedures for CTI dependent flutter in the follow-up period are not considered repeat procedures per CIP.
- **Quality of Life (QoL):** defined as the change of QoL which is assessed by comparing the Atrial Fibrillation Effect on Quality-of-Life (AFEQT™) scores before and at 3, 6 and 12- months after the ablation procedure.
- **Hospitalization for cardiovascular events** through 12-month follow-up compared to 12 months prior to baseline.

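### SAP 7.11.3 analyses the additional-failure-modes endpoint as documented arrhythmia only, so its outputs do not match its definition and antiarrhythmic-drug failure reaches no specified output

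*SAP*

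**What the plan says.** **Definition.** Protocol 7.3.3 starts from freedom from documented symptomatic or asymptomatic arrhythmia in Day 91 to Day 365. It then says: "A subject who meets any of the following criteria will also be deemed an effectiveness failure". The listed criteria are failure to achieve acute procedural success, certain Class I/III AAD use, and repeat ablation (more than one in blanking, or any in the evaluation period). SAP 7.4.4.3 repeats all three. Its AAD criterion covers a new drug and also "taking a previously failed Class I/III AAD at a greater than the highest ineffective historical dose for AF/AFL/AT during the effectiveness evaluation period". A note below it fixes the "start point of the evaluation period of AAD failure, which is Day 105".

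**Analysis.** Under the same endpoint title, SAP 7.11.3 says Kaplan-Meier methods will be used "to characterize the time to first documented (symptomatic and asymptomatic) atrial arrhythmia" in Day 91 to Day 365. For the count it says: "The event-free rate will also be summarized descriptively as the number and percent of subjects free from documented (symptomatic and asymptomatic) atrial arrhythmia".

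**Signs of intent.** The SAP revision history explains the operational AAD rule: "So AAD failure could be systematically evaluated". Protocol Appendix 2, under its off-AAD entry, says: "Class I and III antiarrhythmic drug therapy, higher dose or newly prescribed after procedure is considered as failure". SAP 7.1.3, under Condition 2, says: "Subjects who failed the acute effectiveness endpoint will also be considered failures for the long-term effectiveness endpoint". SAP 7.1.4 sets out when a repeat ablation in the durability subset is a repeat failure.

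**The concern.** The section that specifies the outputs describes a narrower event than the section that defines the endpoint, and does so for both the curve and the percentage. A programmer has to choose between 7.11.3 and 7.4.4.3, and following 7.11.3 to the letter would comply with the SAP.

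Two things are at stake. First, the final report could carry a rate under a label it does not meet: the endpoint built to be stricter than the secondary endpoint could look at least as favourable. Second, AAD failure could go unreported. Acute success has its own analysis in SAP 7.5.2, and repeat ablation has its own displays in 7.11.3. AAD failure after the procedure has neither, so its Day 105 rule would feed nothing.

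**Working it through.** **Step 1. Definition against specified output**

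| Endpoint | Failures in SAP 7.4.4.3 | Output in SAP 7.11.3 | Missing |
|---|---|---|---|
| Additional failure modes | Arrhythmia, acute failure, AAD, repeat ablation | Kaplan-Meier and event-free number and percent, both on documented arrhythmia | Acute failure, AAD and repeat ablation, in both outputs |
| Symptomatic freedom | Symptomatic arrhythmia, acute failure (also protocol 7.3.3) | Kaplan-Meier on symptomatic arrhythmia; no other output spelled out | Acute failure |
| Single Procedural Success | Symptomatic arrhythmia, any repeat procedure for the study arrhythmia | Number and percent of successes; Kaplan-Meier on symptomatic recurrence | Repeat procedure, in the Kaplan-Meier only |
| Repeat ablation due to non-PV targets | Label: repeats due to non-PV targets | Numerator: subjects with non-PV reconnection | Numerator is a different quantity |

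For contrast, the Kaplan-Meier event for the secondary endpoint in SAP 7.10 names acute effectiveness failure alongside recurrence.

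**Step 2. Ordering on the same subjects**

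- Literal 7.11.3 rate: no documented arrhythmia.
- Secondary endpoint (SAP 7.4.3): no documented arrhythmia and no acute failure.
- Defined endpoint (SAP 7.4.4.3): as the secondary, and no AAD failure and no repeat failure.

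Each line adds failures to the one above, so literal ≥ secondary ≥ defined.

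**Step 3. Size at the planning rates**

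Inputs from SAP 6: secondary success 65%, which under 7.4.3 already counts acute failures; acute success 97%, so acute failure is 100% − 97% = 3%. Assumed input: q, the share of all subjects who fail only by AAD or repeat ablation. The documents give no value for q.

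- Literal rate = 65% + the share with acute failure but no recurrence. This is 65% if every acute failure also recurs and 65% + 3% = 68% if none does.
- Defined rate = 65% − q.
- Overstatement = literal − defined = (0 to 3 points) + q.

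| q (assumed) | Defined | Literal | Overstatement |
|---|---|---|---|
| 0% | 65% | 65–68% | 0–3 points |
| 5% | 60% | 65–68% | 5–8 points |
| 10% | 55% | 65–68% | 10–13 points |

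A value of q = 0 is possible: it needs every AAD start or repeat to accompany a documented recurrence or an acute failure. Protocol 13.4 recommends documenting the arrhythmia before a repeat. With at most 135 evaluable subjects, each subject who fails only by AAD or repeat ablation moves the rate by at least 1/135 = 0.74 point.

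**Step 4. A different model**

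Take 65% as the arrhythmia-free rate, with independent failure modes and a share r failing by AAD or repeat among the otherwise event-free. The defined rate is then 0.65 × 0.97 × (1 − r): 63.1% at r = 0, 59.9% at r = 5% and 56.7% at r = 10%. Against 65%, the gaps are 2.0, 5.1 and 8.3 points. This fits SAP 7.4.3 less well, because that section includes acute failure in the secondary endpoint. It leads to the same conclusion: the unknown AAD and repeat share drives the size.

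**The case against.** The best defence is that 7.11.3 is shorthand. The bullet keeps the title with additional failure modes, and SAP 7.4.4 points to 7.11 only for further detail, so 7.4.4.3 could be read as governing. SAP 7.1.3 and 7.1.4 carry acute and repeat failures into long-term effectiveness. SAP 7.11 also promises descriptive statistics on all additional endpoints.

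This stands as evidence of intent. A reader might infer that the sponsor means to drop the three modes, and the documents do not support that. But intent does not change the event that 7.11.3 spells out for both outputs, and nothing in 7.1 or 7.11 carries AAD failure into a specified output. Where the SAP wants a composite event it says so, as in 7.10, or refers to the defined term, as it does for the number and percentage with Single Procedural Success.

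Three further defence points hold:

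- The Single Procedural Success percentage can follow its definition. Only the curve departs from it, and a curve of one component beside that percentage is a lesser matter.
- The non-PV numerator is a wording slip, since its label is correct.
- The Day 105 note already interprets the 3-month-visit start in 7.4.4.3. Only the link to Appendix 2, which uses Day 91 or the visit day, whichever is later, is absent.

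A reader might also infer a bias of 5 to 13 points. That range comes entirely from assumed values of q and is not a finding about this trial.

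**Conclusion.** The mismatch is real and should be corrected before programming. As written, both outputs for the additional-failure-modes endpoint omit three of its failure modes, and AAD failure appears in no specified effectiveness output. The Kaplan-Meier event for symptomatic freedom, the only output spelled out for that endpoint, omits acute failure. The Single Procedural Success curve and the non-PV numerator are minor.

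The ordering in Step 2 follows from the definitions alone, given the same subjects. The size does not: 0 to 3 points at the planning rates if nobody fails only by AAD or repeat ablation, plus that share otherwise.

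A reader might infer that the trial's conclusions are at risk. They are not. SAP 7.11 and protocol 19.4.6 make these endpoints descriptive, so the hypothesis tests, power and study success are untouched, and the secondary endpoint has its own event in 7.10.

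**What to change.** Amend SAP 7.11.3 as follows.

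1. Define each of the three Kaplan-Meier events, and the event-free number and percentage, as *first failure of any kind listed for that endpoint in 7.4.4.3*.
2. Prespecify event dates separately for each endpoint. For additional failure modes, a blanking-period repeat counts only from the second repeat, and any repeat counts in the evaluation period. For Single Procedural Success, the first repeat for the study arrhythmia counts. State the date given to acute failure (the index procedure or the start of the evaluation period; either is workable if fixed in advance) and to AAD failure. SAP 7.10 also gives no date for acute failure and could take the same convention.
3. Cross-reference the Day 105 AAD start to protocol 7.3.3 and Appendix 2, so that the three texts are reconciled.
4. Reword the non-PV numerator to count subjects whose repeat ablation was due to non-PV targets.

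The cost is SAP wording only. Acute outcome, cardiac medication and repeat ablations are already collected. The downside is a descriptive event-free rate that may be less favourable.

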13.4 Repeat Ablation Procedures

Repeat procedures may be performed at the discretion of the investigator. It is highly recommended to collect arrhythmia documentation (in example documented recurrences) before performing a repeat procedure.

Repeat procedures **during the blanking period** (\leq 90 days post index ablation procedure) must be conducted with the investigational device, with or without focal touch-up, if the arrhythmia is due to PV triggers. If the arrhythmia is due to non-PV triggers and the subject is treated with a commercially available ablation catheter and generator, the subject will be excluded from the long- term effectiveness cohort. Procedures for CTI dependent flutter in the follow up period are not considered repeat procedures per CIP.

Repeat procedures performed **after the blanking period** (\geq 90- 365days post index ablation procedure) may be managed per investigator discretion using a commercially available ablation catheter and generator.

For the repeat procedures, the investigator must collect and provide information on location of reconnections of PVs and in case of atrial flutter recurrence, confirm if CTI dependent flutter or not. The follow-up schedule will remain based on the index ablation procedure.

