- Condition 4: The **use of the investigational ablation system or commercial RF devices for the ablation of the CTI line to treat documented typical atrial flutter**, identified prior to or during the procedure, is allowed. As the investigational devices are the primary devices used for PV region ablation, these subjects who undergo CTI line ablation will be included in the analyses for acute and long-term effectiveness endpoints.
- In cases where commercial system other than available commercial BWI RF systems are used for repeat ablation during blanking, these subjects will be excluded from the long-term effectiveness analyses unless already failed long-term effectiveness endpoints prior to the repeat ablation.

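### SAP 7.11.3 specifies the non-study-catheter PVI rates for the index procedure only, although SAP 7.4.4.3 defines the endpoint to include repeat procedures in blanking

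*SAP*

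**What the plan says.** **Definition.** SAP 7.4.4.3 describes use of a non-study device "for the purpose of PVI (i.e., touch-up) and/or for the ablation of left atrial non-PV AF targets", and closes the same sentence with the time frame "during index ablation procedure or within-lanking repeat procedures" (a typing slip for blanking).

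**Formulas.** SAP 7.11.3 gives two PVI rates. The vein-level rate is headed "Rate of ablation by NSC for PVI among all targeted pulmonary veins during index procedure" and the subject-level rate "Rate of ablation by NSC for PVI among subjects during index procedure". The next item, on left atrial non-PV targets, covers the index procedure and repeats in blanking. Above the formulas, one sentence says that subjects and veins ablated for PVI with a non-study catheter will be summarized; it sets no time limit.

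**Protocol.** In Protocol 7.3.3 the PVI bullet reads "PVI (i.e., touch-up) among all clinically relevant targeted PVs and by subject" and has no time limit. The phrase "during index ablation procedure or for repeat procedures during blanking period" stands on the non-PV bullet only.

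**Blanking repeats.** Under Protocol 13.4, blanking repeats for PV triggers "must be conducted with the investigational device, with or without focal touch-up". The last bullet of SAP 7.1.3 removes a subject from the long-term analyses where a "commercial system other than available commercial BWI RF systems are used for repeat ablation during blanking", unless that subject has already failed.

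**The concern.** The formulas in SAP 7.11.3 do not compute the endpoint as SAP 7.4.4.3 defines it. The PVI half has been narrowed to the index procedure without explanation, while the non-PV half has not.

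What is left out bears on the secondary endpoint. A subject whose veins reconnect and are touched up in blanking with a commercial BWI RF system can reach Day 365 free of arrhythmia and be counted as a success of the study system. SAP 7.1.3 (Condition 3) excludes subjects ablated outside the PV region with commercial RF devices because the effects of the two systems would be mixed. The same mixing arises when a commercial device completes PVI in blanking, but there the subject stays in and no specified rate shows it. A reader of the final report could not tell how many 12-month successes had PVI help from another device.

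**Working it through.** The plan states no figure for this rate, so the check is mainly a comparison of texts.

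**Step 1: scope of each statement**

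| Place | PVI | Left atrial non-PV targets |
|---|---|---|
| Protocol 7.3.3 | no time limit stated | index and blanking repeats |
| SAP 7.4.4.3 | index and blanking repeats | index and blanking repeats |
| SAP 7.11.3, introductory sentence | no time limit stated | not covered |
| SAP 7.11.3, formulas | index only (vein and subject) | index and blanking repeats |

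The two PVI formulas are the only entries restricted to the index procedure.

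**Step 2: path of a subject touched up for PVI in blanking with a commercial BWI RF system**

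- Acute failure: not triggered. Success is judged when the index procedure ends (Protocol 7.3.1, SAP 7.4.2).
- Exclusion from the long-term analyses: not triggered by the last bullet of SAP 7.1.3, which reaches only other commercial systems.
- Secondary endpoint failure: not triggered by the touch-up. SAP 7.4.3 requires an acute failure or a qualifying AF, AT or AFL episode in Day 91-365.
- Endpoint with additional failure modes: one blanking repeat is not a failure; more than one is needed (SAP 7.4.4.3).
- Repeat-ablation rates in SAP 7.11.3: these give repeats by period, reconnection by vein and by subject, and non-PV targets. None gives the device used for PVI.

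The subject can therefore be a 12-month success while no specified rate shows the device.

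**Step 3: size**

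With the planned 135 subjects (SAP section 6) all ablated for PVI, each affected subject adds 1/135 = 0.74 percentage points to a combined subject-level rate.

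The table uses assumed counts, with no subject in both columns. The index-only rate is i/135 and the combined rate is (i + b)/135.

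| Index use, i | Blanking only, b | Index-only rate | Combined rate |
|---|---|---|---|
| 0 | 1 | 0% | 1/135 = 0.7% |
| 0 | 3 | 0% | 3/135 = 2.2% |
| 0 | 5 | 0% | 5/135 = 3.7% |
| 0 | 10 | 0% | 10/135 = 7.4% |
| 4 | 3 | 4/135 = 3.0% | 7/135 = 5.2% |
| 4 | 10 | 4/135 = 3.0% | 14/135 = 10.4% |

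The documents give neither i nor b, so these rows show only how the two rates separate.

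**Step 4: the secondary test, as background**

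SAP section 6 plans 100 subjects with 10% missing, which leaves 90. In the exact one-sided test of 50%, the smallest success count with tail probability at most 0.025 is 55 (exact alpha 0.0223). Power at 65% is 81.2%, so the stated figure above 80% is reproduced. Reporting the device changes neither who enters this test nor its rule.

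**The case against.** **The formulas may follow the protocol.** Protocol 7.3.3 attaches the time frame to the non-PV bullet only, and elsewhere the protocol speaks of clinically relevant targeted veins in connection with the index procedure. On that reading SAP 7.4.4.3 merged two bullets, and the formulas are right. This is a fair reading, and it means the wider PVI scope rests on one SAP sentence. The SAP then still contradicts itself and has to say which scope applies.

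**A reader might infer that blanking touch-ups will never be reported.** The documents do not support that. The introductory sentence in SAP 7.11.3 is untimed and could cover them, and the table layouts are not available. What can be said is that no rate or denominator is specified.

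**A reader might infer that any other device leaves the subject in the 12-month analysis.** It does not. Other commercial systems lead to exclusion unless the subject has already failed, and Protocol 13.4 excludes subjects treated in blanking for non-PV triggers with a commercial catheter and generator.

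**A reader might infer that the protocol expects touch-up with another device.** Protocol 13.4 permits focal touch-up and does not name the device; the link to a non-study device comes from the wording of Protocol 7.3.3. A PV-triggered repeat done wholly with a commercial system would depart from 13.4 and might cost the subject a place in the per-protocol set, whose list of major deviations is open-ended. The point is firmest for a permitted touch-up with a BWI RF system.

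**Much is already visible.** The percentage with a blanking repeat caps the number of subjects affected through repeat procedures, and Single Procedural Success counts a repeat for the study arrhythmia as a failure. Both are true, but the second concerns symptomatic recurrence only and neither identifies the device.

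**Conclusion.** The mismatch stands. The two PVI formulas in SAP 7.11.3 cover less than the endpoint defined in SAP 7.4.4.3. Subjects touched up for PVI in blanking with a commercial BWI RF system can count as 12-month successes without the device being shown. This rests on the SAP sentence that puts PVI and non-PV use under one time frame, and on such subjects remaining in the per-protocol set.

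The firm size is 0.74 points per affected subject out of 135. The documents give no basis for the number of such subjects. A reader might also set this against an index rate of at most 3%, taken from the assumed 97% acute success. That does not follow: under Condition 1 of SAP 7.1.3, PVI completed with commercial RF for reasons unrelated to the study system is excluded from the acute analysis rather than counted as a failure, yet it is still non-study-catheter use at index.

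The endpoint is descriptive (SAP 7.4.4 and 7.11). No hypothesis test, alpha, power or primary conclusion is affected, so this is a minor reporting point.

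**What to change.** In SAP 7.11.3, give the non-study-catheter rate for PVI, by vein and by subject:

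- (a) at the index procedure, as now;
- (b) at repeat procedures in blanking (up to Day 90), with subjects and veins treated for PVI at those repeats as denominator;
- (c) combined: subjects (or veins) ablated for PVI with a non-study catheter at index or at any blanking repeat, each counted once, over all those ablated for PVI.

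Add the number of subjects in (b) who are in the 12-month analysis and the number of those counted as successes. If the sponsor means the PVI part to be index-only, SAP 7.4.4.3 should say so; the two 12-month counts are still worth reporting.

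State also whether (b) includes PV ablations at the Day 60-90 durability re-map, since SAP 7.1.4 does not treat these as repeat procedures when no arrhythmia is documented.

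The cost is a SAP clarification and a few table rows. The protocol's schedule of events already provides for information on any repeat ablation, and the exclusion rule in SAP 7.1.3 cannot be applied without knowing the system used. The sponsor should confirm that the case report form records the device for each vein.
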